### **2.4.1 Time point response**

It is assumed that at each protocol specified time point, a response assessment occurs. **Table A-1** on the next page provides a summary of the overall response status calculation at each time point for patients who have measurable disease at baseline.

### **2.4.2 Missing assessments and inevaluable designation**

When no imaging/measurement is done at all at a particular time point, the patient is not evaluable (NE) at that time point. If only a subset of lesion measurements is made at an assessment, usually the case is also considered NE at that time point, unless a convincing argument can be made that the contribution of the individual missing lesion(s) would not change the assigned time point response. This would be most likely to happen in the case of PD. For example, if a patient had a baseline sum of 50 mm with three measured lesions and at follow-up only two lesions were assessed, but those gave a sum of 80 mm, the patient will have achieved PD status, regardless of the contribution of the missing lesion.

### **2.4.3 Best overall response: all time points**

The *best overall response* is determined once all the data for the patient is known.

**Table A-1** **Time point response: patients with target (+/- non-target) disease**

| Target lesions    | Non-target lesions          | New lesions | Overall response |
|-------------------|-----------------------------|-------------|------------------|
| CR                | CR                          | No          | CR               |
| CR                | Non-CR/non-PD               | No          | PR               |
| CR                | Not evaluated               | No          | PR               |
| PR                | Non-PD or not all evaluated | No          | PR               |
| SD                | Non-PD or not all evaluated | No          | SD               |
| Not all evaluated | Non-PD                      | No          | NE               |
| PD                | Any                         | Yes or No   | PD               |
| Any               | PD                          | Yes or No   | PD               |
| Any               | Any                         | Yes         | PD               |

CR = complete response, PR = partial response, SD = stable disease, PD = progressive disease, and NE = inevaluable.

*Best response determination in trials where confirmation of complete or partial response IS required:* Complete or partial responses may be claimed only if the objective response is confirmed on a follow-up scan obtained no less than 4 weeks after the initial scan demonstrating an objective response. In this circumstance, the best overall response can be interpreted as in **Table A-2**.

**Table A-2** **Best overall response when confirmation of CR and PR required**

| Overall response
First time point | Overall response
Subsequent time point | BEST overall response                                           |
|--------------------------------------|-------------------------------------------|-----------------------------------------------------------------|
| CR                                   | CR                                        | CR                                                              |
| CR                                   | PR                                        | SD, PD or PR a                                       |
| CR                                   | SD                                        | SD                                                              |
| CR                                   | PD                                        | SD                                                              |
| CR                                   | NE                                        | SD                                                              |
| PR                                   | CR                                        | PR                                                              |
| PR                                   | PR                                        | PR                                                              |
| PR                                   | SD                                        | SD                                                              |
| PR                                   | PD                                        | SD provided minimum criteria for SD duration met, otherwise, PD |
| PR                                   | NE                                        | SD provided minimum criteria for SD duration met, otherwise, NE |
| NE                                   | NE                                        | NE                                                              |

CR = complete response, PR = partial response, SD = stable disease, PD = progressive disease, and NE = inevaluable.

a If a CR is *truly* met at first time point, then any disease seen at a subsequent time point, even disease meeting PR criteria relative to baseline, makes the disease PD at that point (since disease must have reappeared after CR). Best response would depend on whether minimum duration for SD was met. However, sometimes 'CR' may be claimed when subsequent scans suggest small lesions were likely still present and in fact the patient had PR, not CR at the first time point. Under these circumstances, the original CR should be changed to PR and the best response is PR.

## **Special notes on response assessment**

When nodal disease is included in the sum of target lesions and the nodes decrease to ‘normal’ size (< 10 mm), they may still have a measurement reported on scans. This measurement should be recorded even though the nodes are normal in order not to overstate progression should it be based on increase in size of the nodes. As noted earlier, this means that patients with CR may not have a total sum of ‘zero’ on the case report form (CRF).

Patients with a global deterioration of health status requiring discontinuation of treatment without objective evidence of disease progression at that time should be reported as ‘symptomatic deterioration’. Every effort should be made to document objective progression even after discontinuation of treatment. Symptomatic deterioration is *not* a descriptor of an objective response: it is a reason for stopping study therapy. The objective response status of such patients is to be determined by evaluation of target and non-target disease as shown in **Table A-1** and **Table A-2**.

For equivocal findings of progression (e.g., very small and uncertain new lesions; cystic changes or necrosis in existing lesions), treatment may continue until the next scheduled assessment. If at the next scheduled assessment, progression is confirmed, the date of progression should be the earlier date when progression was suspected.

## **2.5 Confirmation/Duration of response**

### **2.5.1 Confirmation**

Objective responses should be confirmed by CT and/or MRI scans obtained no less than 4 weeks after the original scan.

### **2.5.2 Duration of overall response**

The duration of overall response is measured from the time measurement criteria are first met for CR/PR (whichever is first recorded) until the first date that recurrent or progressive disease is objectively documented (taking as reference for progressive disease the smallest measurements recorded on study). The duration of overall complete response is measured from the time measurement criteria are first met for CR until the first date that recurrent disease is objectively documented.

### **2.5.3 Duration of stable disease**

Stable disease is measured from the start of the treatment until the criteria for progression are met, taking as reference the *smallest sum on study* (if the baseline sum is the smallest, this is the reference for calculation of PD).

---

**Appendix 6                    Brief Pain Inventory-Short Form (BPI-sf)**

---

Table 1	Response Rates and 95% Confidence Intervals.....	15
Table 2	Censoring Rules for Primary Progression-free Survival Analysis	24

LIST OF FIGURES

Figure 1	Overall Study Design.....	13
Figure 2	MGC018 Monotherapy Dosing Schedule (Module A).....	14
Figure 3	MGC018 and MGC012 Combination Dosing Schedule (Module B)	14

LIST OF ABBREVIATIONS

ADA	Anti-drug antibodies
AUC	Area under the curve
BOR	Best overall response
BPI-sf	Brief Pain Inventory-short form
CI	Confidence interval
CR	Complete response
CSR	Clinical study report
CT	Computed tomography
CTCAE	Common terminology criteria for adverse events
DLT	Dose limiting toxicity
DoR	Duration of response
ECG	Electrocardiogram
eCRF	Electronic case report form
EOTV	End of treatment visit
ICD	Immunological cell death
IFN γ	Interferon gamma
IHC	Immunohistochemistry
IV	Intravenous
LVEF	Left ventricular ejection fraction
MedDRA	Medical Dictionary for Regulated Activities
MAD	Maximum administered dose
mCRPC	Metastatic castration-resistant prostate carcinoma
MRI	Magnetic resonance imaging
MSI-H	Microsatellite instability-high

MTD	Maximum tolerated dose
NCI	National Cancer Institute
NE	Not evaluable
NSCLC	Non-small cell lung cancer
ORR	Objective response rate
OS	Overall survival
PFS	Progression-free survival
PD	Progressive disease
PD-1	Programmed death-1
PD-L1	Programmed death ligand-1
PK	Pharmacokinetic(s)
PR	Partial response
PRO	Patient-reported outcome
PSA	Prostate-specific antigen
PT	Preferred term
Q3W	Once every 3 weeks
RECIST	Response Evaluation Criteria in Solid Tumors
rPFS	radiographic progression-free survival
SAE	Serious adverse event
SAP	Statistical analysis plan
SCCHN	Squamous cell carcinoma of the head and neck
SD	Stable disease
SOC	System organ class
SPP	Statistical programming plan
SSE	Symptomatic skeletal event

TCR	T cell receptor
TEAE	Treatment emergent adverse event
TNBC	Triple-negative breast cancer

1 INTRODUCTION

This study is an open-label, Phase 1/2, dose escalation, and cohort expansion study designed to characterize the safety, tolerability, pharmacokinetics (PK), pharmacodynamics, immunogenicity, and preliminary antitumor activity of MGC018 alone (Module A) and in combination with MGA012 (Module B), each administered by IV infusion, in participants with advanced solid tumors.

This statistical analysis plan (SAP) describes in detail the statistical methods to be used for analysis of the primary and secondary efficacy endpoints, the safety endpoints, and the PK parameters to be collected from this study.

2 STUDY OBJECTIVES

2.1 Primary Objective

To characterize the safety, tolerability, dose-limiting toxicities (DLTs), and maximum tolerated dose (MTD) or maximum administered dose (MAD) (if no MTD is defined) for MGC018 administered as monotherapy or in combination with MGA012, each administered intravenously (IV), in participants who have relapsed/refractory, unresectable locally advanced, or metastatic solid tumors.

2.2 Secondary Objectives

- To characterize the PK and immunogenicity of MGC018 alone and in combination with MGA012.
- To describe antitumor activity of MGC018 administered as monotherapy or in combination with MGA012 in participants with advanced solid tumors using Response Evaluation Criteria in Solid Tumors version 1.1 (RECIST v1.1).
- To describe the radiographic progression-free survival (rPFS) in metastatic castration-resistant prostate carcinoma (mCRPC).
- To describe the prostate-specific antigen (PSA) response rate and the best PSA percent change in mCRPC.

2.3 Exploratory Objectives

- To explore patient-reported outcome (PRO) using the Brief Pain Inventory-short form (BPI-sf) in Cohort Expansion (Module A).
- To explore effect of MGC018 on symptomatic skeletal events (SSEs) in participants with mCRPC in Cohort Expansion (Module A).
- To explore the relationships between PK, pharmacodynamics of MGC018 alone and in combination with MGA012, and antitumor activity (Modules A and B).
- To explore the impact of MGC018 alone and in combination with MGA012 on progression-free survival (PFS) and overall survival (OS) in participants with advanced solid tumors (Modules A and B).
- To determine programmed death-ligand 1 (PD-L1) expression via immunohistochemistry (IHC) staining of formalin-fixed, paraffin-embedded tumor biopsy specimens on archival tissue (Module B) and on optional paired tumor biopsy specimens (pre/on-treatment post Cycle 1 biopsies) in Cohort Expansion (Modules A and B).
- To explore the relationship between B7-H3 expression (H-score) and clinical response using a qualified B7-H3 IHC assay (Modules A and B).

- To assess whether MGC018 in combination with MGA012 induces immunological cell death (ICD) within optional paired tumor biopsy specimens (pre/on-treatment post cycle 1 biopsies) from participants in Cohort Expansion (Module B) as assessed by IHC.
- To assess whether MGC018 in combination with MGA012 modulates immune cell subset phenotype (including PD-1 expression) (Module B).
- To explore whether MGC018 modulates T cell response within optional paired tumor biopsy specimens (pre/on-treatment post Cycle 1 biopsies) from participants in Cohort Expansion (Modules A and B) as assessed by IHC and/or T cell receptor (TCR) spectratyping.
- To assess whether MGC018 alone or in combination with MGA012 induces an interferon gamma (IFN γ) gene expression signature in the optional paired tumor biopsy specimens (pre/on-treatment post Cycle 1 biopsies) from participants in Cohort Expansion (Modules A and B) via transcript profiling.
- To explore serum biomarkers including, but not limited to, IFN γ protein signature, in the peripheral circulation within the Cohort Expansion only (Modules A and B).
- To assess whether MGC018 modulates serum cytokine levels in Dose Escalation and Cohort Expansion phases (Modules A and B).
- To determine MGA012 receptor occupancy on immune cells in participants treated with the combination of MGC018 and MGA012 (Module B only).

The results of the exploratory objectives may not be included in the Clinical Study Report (CSR) or database lock unless they represent meaningful findings.

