- To determine MGA012 receptor occupancy on immune cells in participants treated with the combination of MGC018 and MGA012 (Module B only).

The results of the exploratory objectives may not be included in the Clinical Study Report or database lock unless they represent meaningful findings.

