6.7.2 Analyses of Time-to-event Endpoints

6.7.2.1 Analyses of Progression-free Survival

The Kaplan-Meier method will be applied to estimate PFS curve, median PFS, and PFS rates at 3 and 6 months. The method of Brookmeyer and Crowley (1) will be used to construct 95% CI for median PFS. The 95% CIs for PFS rate will be calculated by normal approximation after log(-log) transformation.

For patients who are not known to be dead or progressed at the time of data cut-off for PFS analysis, the PFS will be censored at the date of the last tumor assessment. For primary PFS analysis, Table 2 describes the censoring rules.

Table 2 Censoring Rules for Primary Progression-free Survival Analysis

Situation	Date	Outcome
No baseline tumor assessments	First dose date	Censored
Death prior to first scheduled tumor assessment	Date of death	Progressed
No post-baseline tumor assessments in absence of death prior to first scheduled tumor assessment	First dose date	Censored
Documented progression	Date of progression	Progressed
Initiation of alternative anti-cancer treatments in absence of documented progression	Date of last tumor assessment prior to initiation of such treatment	Censored
Death or documented progression immediately after missing two or more consecutive scheduled tumor assessments	Date of last tumor assessment prior to missed assessments	Censored

PFS will be analyzed by tumor type when sample size warrants. A sensitivity analysis for PFS may be performed to assess the robustness of above primary PFS analysis. For this sensitivity analysis, the censoring rules are the same as in **Table 2** except that the documented progression or death will be considered as an event, regardless when it occurs during the study.

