6.7.3 Subgroup and B7-H3 Expression Analyses

Subgroup analysis of efficacy (e.g., objective response rate, PFS and OS) may be conducted based on the following biomarkers:

Microsatellite instability-high (MSI-H) status

BRCA-1 mutation

BRCA-2 mutation

BRAF mutation (melanoma only)

Human papilloma viral status (SCCHN only)

The relationship between B7-H3 expression IHC score and clinical response will be explored.

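### Whether exploratory results, including PFS, OS, SSE and BPI-sf, enter the CSR or database lock may depend on the results themselves, under an undefined criterion that conflicts with SAP 6.7 and 7

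*SAP*

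**What the plan says.** The sentence closing the list of exploratory objectives is the same in both documents apart from an abbreviation. SAP 2.3 reads: "The results of the exploratory objectives may not be included in the Clinical Study Report (CSR) or database lock unless they represent meaningful findings". Protocol 3.3 reads: "The results of the exploratory objectives may not be included in the Clinical Study Report or database lock unless they represent meaningful findings". Neither document defines *meaningful*, says who decides or when, or exempts any endpoint.

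The list above that sentence in SAP 2.3 is not confined to research assays. One objective begins "To explore the impact of MGC018 alone and in combination with MGA012 on progression-free survival (PFS) and overall survival (OS" and covers Modules A and B. Two others cover SSE in mCRPC and BPI-sf pain, both in the Module A expansion. The relation of B7-H3 expression to response is listed as well.

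The analysis sections carry no such condition. For PFS, SAP 6.7.2.1 says "The Kaplan-Meier method will be applied to estimate PFS curve, median PFS, and PFS rates at 3 and 6 months". SAP 6.7.2.3 (OS), 6.7.5 (SSE) and 6.7.6 (BPI-sf) are equally firm, and SAP 7 plans the CSR tables, listings and figures from the analyses the SAP describes.

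**The concern.** A rule that looks at the result before deciding whether to report it can filter the evidence. Expansion cohorts have up to 16 participants, so cohort estimates vary widely by chance. Outside mCRPC, where rPFS and the PSA endpoints do not apply, PFS and OS are the time-to-event evidence covering all treated participants. If disappointing results could be left out, the remaining estimates would tend to be too high and the reader would not know how many had been looked at. Naming the database lock as well as the CSR adds to the difficulty, since data specific to an omitted analysis could also fall outside the lock.

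**Working it through.** **1. The passages side by side**

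| Endpoint | Status (SAP 2.2, 2.3) | Analysis commitment | Reached by the sentence? |
|---|---|---|---|
| PFS | Exploratory | SAP 6.7.2.1; Protocol 14.6.3: unconditional | Yes |
| OS | Exploratory | SAP 6.7.2.3; Protocol 14.6.3: unconditional | Yes |
| SSE (mCRPC) | Exploratory | SAP 6.7.5; Protocol 14.6.4.3: unconditional | Yes |
| BPI-sf | Exploratory | SAP 6.7.6; Protocol 14.6.5: unconditional | Yes |
| ORR, rPFS, PSA response | Secondary | SAP 6.7.1, 6.7.5 | No |

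Where SAP 6.7.2 does attach conditions, they concern the amount of data: PFS and OS by tumour type if the sample size allows, and DoR if there are enough responders. Only the sentence in SAP 2.3 and Protocol 3.3 makes inclusion depend on what was found. A team could analyse PFS as SAP 6.7 requires and still omit it from the CSR under SAP 2.3, but that would contradict SAP 7.

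**2. The plan's own figures**

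The documents attach no number to the sentence. The nearest checkable figures are the exact 95% intervals for n = 16 (SAP Table 1). Clopper-Pearson reproduces all six; for example, 4/16 = 25.0% gives 7.3% to 52.4%. That width shows how far one cohort can move by chance.

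**3. Illustration of selection**

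Input from the documents: 5 + 3 = 8 expansion cohorts of up to 16 (SAP 3.2). Removing the two mCRPC cohorts leaves 6, if the tumour type still to be chosen for Module B is not mCRPC.

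Assumptions: full cohorts of 16, one true 6-month PFS rate p shared by all six, no censoring, independent cohorts, and each cohort reported only if its estimate reaches a cut c.

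Let X ~ Bin(16, p) and let r be the smallest whole number at or above 16c.

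- Chance that one cohort qualifies: P1 = P(X ≥ r)
- Chance that at least one of six qualifies: 1 − (1 − P1)^6
- Mean reported rate: E[X | X ≥ r] / 16

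For p = 30% and c = 40%: 16 × 0.40 = 6.4, so r = 7 and P1 = 0.175. Then 1 − 0.825^6 = 0.69, and the mean reported rate is 47.6%.

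The last column is coverage of the true rate among reported cohorts, using the SAP's log(-log) interval. Without censoring this is S^exp(±1.96 × se), with S = X/16 and se = √[(1 − S)/(16S)] / |ln S|.

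| True p | Cut c | r | P1 | At least 1 of 6 | Mean reported | Coverage |
|---|---|---|---|---|---|---|
| 30% | 30% | 5 | 0.550 | 0.99 | 38% | 0.99 |
| 30% | 40% | 7 | 0.175 | 0.69 | 48% | 0.96 |
| 30% | 50% | 8 | 0.074 | 0.37 | 53% | 0.90 |
| 20% | 30% | 5 | 0.202 | 0.74 | 35% | 0.96 |
| 20% | 40% | 7 | 0.027 | 0.15 | 46% | 0.74 |

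The mean reported rate exceeds the truth in every row. Coverage falls below 95% only when the cut is far above the true rate.

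**The case against.** The strongest reply is that the sentence is permissive and that SAP 6.7 and 7 already promise these analyses and CSR outputs built on them. Protocol 14 adds that the SAP governs the analysis. On that reading, the sentence is loose wording meant for assay work that may not be ready at lock. The trial is also an open-label Phase 1/2 study with a safety and dose-finding primary objective and descriptive efficacy. This limits the importance of the point, but it does not settle which passage prevails, because the conflicting sentence is in the SAP too.

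Several stronger readings are tempting, and the documents do not support them:

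- **That whatever appears is favourable by selection.** Omission is allowed, not required, and *meaningful* is not the same as favourable: clearly poor survival or worsening pain could also qualify.
- **That the biomarker subgroups in SAP 6.7.3 add a multiplicity problem through this sentence.** The text there is "Subgroup analysis of efficacy (e.g., objective response rate, PFS and OS) may be conducted based on the following biomarkers". Those subgroups are not listed exploratory objectives, ORR belongs to a secondary objective, and no test is planned. Of that section, only B7-H3 against response falls under the sentence.
- **That PFS and OS are the only time-to-event evidence outside mCRPC.** DoR is another, although it covers responders only and is analysed only if there are enough of them.
- **That tumour data could go unlocked.** PFS uses the RECIST assessments that the secondary ORR needs in any case.

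The illustration is also open to challenge. PFS and OS form one objective across tumours and modules, and nothing in the sentence describes dropping single cohorts. A common true rate, no censoring and the cut are all assumed, and the result depends heavily on the cut.

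**Conclusion.** The point stands as an internal conflict together with an undefined, result-dependent reporting rule. It affects PFS, OS, SSE, BPI-sf and the remaining exploratory objectives. It is more than a missing detail, because the stated condition for inclusion is the finding itself.

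Its effect cannot be sized from the documents, since *meaningful* has no threshold. In the central case above, the mean reported rate would exceed the truth by about 18 percentage points (47.6% − 30%). That shows what could happen under cohort-by-cohort omission, not what will happen. A reader might also infer that the 95% intervals necessarily fail; the coverage column shows this depends on the cut, so the most that can be said is that they may not cover as stated. The change should be made, but the primary and secondary conclusions do not depend on it.

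**What to change.** In SAP 2.3 and, at the next amendment, in Protocol 3.3, replace the sentence with:

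> The PFS, OS, SSE and BPI-sf analyses described in SAP 6.7 will be included in the database lock and reported in the CSR as planned, whatever the result. Any B7-H3 or biomarker subgroup analysis carried out will be reported, with the number examined. Exploratory assay data not available at database lock may be reported separately; this will depend on data availability, not on the result.

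This keeps a legitimate reason for deferral, removes the conflict with SAP 6.7 and 7, and leaves the sample-size condition for analyses by tumour type in place. The biomarker subgroups are included because they are optional and the SAP does not require a count of those examined. The clinical analyses are already specified, so the downside is a slightly longer CSR that also shows unfavourable exploratory results.
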